### 5.3. Secondary Efficacy Endpoints

The secondary efficacy endpoints are:

- Clinical response rate (CRR, i.e. MR or better)
- Very good partial response (VGPR) or better rate
- Duration of response (DOR)
- Time to response (TTR)
- Progression-free survival (PFS)
- Overall survival (OS)

#### 5.3.1. Definition

##### Clinical response rate:

CRR is defined as the proportion of subjects who achieve MR or better according to the modified IVth IWWM (NCCN 2019) criteria as assessed by the investigator.

##### Very good partial response (VGPR) or better rate:

VGPR or better rate is defined as the proportion of subjects who achieve VGPR or better according to the modified IVth IWWM (NCCN 2019) criteria as assessed by the investigator.

**Duration of response (DOR):**

DOR is defined as duration from the date of initial documentation of a response (PR or better) to the date of first documented evidence of progressive disease, death or date of censoring if applicable, for responders (PR or better) as assessed by the investigator. DOR will be right censored based on [Table 2](#) for all responders:

**Table 2: Date of Event or Censoring for Duration of Response/Progression Free Survival**

Situation	Date of DOR/PFS event or Censoring	Outcome
Death or disease progression occurred regardless of the use of subsequent antineoplastic therapy prior to documented death or disease progression.	Earliest date of adequate disease assessment documenting disease progression or date of death, whichever occurs first.	Event
Not known to have progressed or died at the data analysis cutoff date (this includes subjects who were known to have progressed or died after the data analysis cutoff date)	Date of last adequate disease assessment showing no evidence of disease progression.	Censored

**Time to response:**

Time to response is defined as the time from the date of first dose to the date of initial documentation of a response (PR or better) for responders.

**Progression-free survival (PFS):**

PFS is defined as duration from the date of first dose to the date of disease progression or death, whichever is first reported, assessed according to the modified VIth IWWM (NCCN 2019)

criteria. The same censoring rules for DOR are used for PFS.

**Overall survival (OS):**

OS is measured from the date of first dose to the date of the subject's death from any cause. OS will be right censored if no death has occurred at the data analysis cutoff date.

**5.3.2. Analysis Methods**

The all treated population will be used for all secondary efficacy endpoints.

CRR rate and VGPR or better rate will be analyzed with the exact 2-sided 90% CI based on binomial distribution.

The DOR for responders will be calculated by the Kaplan-Meier method descriptively. Median DOR and the corresponding 95% confidence interval will be provided if estimable with Kaplan-Meier plot.

Time to response will be summarized descriptively for responders only.

Progression-free survival will be evaluated descriptively using Kaplan-Meier method. Median PFS and the corresponding 95% CI will be provided if estimable with Kaplan-Meier plot. PFS rates at 1-year, 2-year and 3-year landmarks will also be estimated using Kaplan-Meier.

OS will be evaluated in a similar fashion as DOR and PFS.

## 6. SAFETY

All safety analyses will be based on the safety analysis set and based on actual treatment received, unless otherwise specified.

For all continuous safety variables, descriptive statistics will include the N, mean, standard deviation, median, minimum, and maximum. Categorical variables will be summarized using frequency counts and percentages.

### 6.1. Adverse Events

The verbatim terms used in the CRF by investigators to identify adverse events will be coded using the Medical Dictionary for Regulatory Activities (MedDRA). Treatment-emergent adverse events (TEAEs) are those adverse events occurring after the first dose of study drugs and within 30 days following the last dose of study drug or initiation of subsequent antineoplastic treatment, whichever occurs earlier; any adverse event that is considered study drug-related regardless of the start date of the event; or any adverse event that is present at baseline but worsens after the first administration of study drug in severity or is subsequently considered drug-related by the investigator. If the event occurs on the day of the initial administration of study agent, and either event time or time of administration are missing, then the event will be assumed to be treatment emergent. If the event date is recorded as partial or completely missing, then the event will be considered to be treatment emergent unless it is known to be prior to the first administration of study agent based on partial onset date or resolution date. All reported treatment-emergent adverse events will be included in the analysis. For each adverse event, the number and percentage of subjects who experience at least 1 occurrence of the given event will be summarized.

Summary tables will be provided for treatment-emergent adverse events:

- Overall summary of all TEAEs
- TEAEs by System Organ Class (SOC), preferred term (PT) and toxicity grade 3 or higher
- TEAE with frequency of at least 10% by SOC, PT and toxicity grade 3 or higher
- Drug-related TEAEs by SOC, PT and toxicity grade 3 or higher
- Serious TEAEs by SOC, PT and toxicity grade 3 or higher
- TEAEs leading to dose modification (including dose interruption and dose reduction) by SOC, PT and toxicity grade 3 or higher
- TEAEs leading to discontinuation of study drug by SOC, PT and toxicity grade 3 or higher
- TEAEs leading to death by SOC and PT
- TEAEs by SOC, PT and toxicity by period
- TEAE of interest for COVID-19 infection by PT and toxicity grade
- Serious TEAE of interest for COVID-19 infection by PT and toxicity grade

- TEAE of interest for COVID-19 infection leading to death by PT

In addition to the summary tables, listings will be provided as appropriate.

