### **12.1.5. Other Malignancies**

In addition to all routine AE reporting, all new malignancies, including solid tumors, skin malignancies and hematologic malignancies, are to be reported for the duration of study treatment and during any protocol-specified follow-up periods including post-progression follow-up for overall survival.

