## **2.10. Imputation Rules for Missing Date**

In general, imputation of missing dates will be made for AE onset date, AE resolution date, start and end dates of prior and concomitant and subsequent therapies and date of initial diagnosis according to the following rules.

- If the date is completely missing, no imputation will be made.
- If the year is missing, then no imputation will be made.
- If only the year is presented but the month and day are missing, then June 30th will be used.
- If only the day is missing but the year and month are available, then the 15th of the month will be used.

In addition, for date of initial diagnosis, the imputed date will be adjusted sequentially using the following steps:

- If only the day is missing:
  - if month and year of start of 1st line of prior therapy are the same year and month of diagnosis, and day of start date of 1st line of prior therapy is available, then the day of start date of 1st line of prior therapy will be used.
  - otherwise, the 15th of the month will be used.
- If both month and day are missing:
  - if year of diagnosis is the same as year of start of 1st line of prior therapy, and month information is available for start date of the 1st line of prior therapy, the month of start date of 1st line of prior therapy will be used.
    - if day of start date of 1st line of prior therapy is available, then the day of start date of 1st line of prior therapy will be used.
    - otherwise, the 15th of the month will be used.
  - otherwise, June 30th will be used.
- If the imputed date for initial diagnosis is on or after the first dose date, then first dose date - 1 day will be used.

In addition, for date of prior and subsequent therapies, the imputed date will be adjusted sequentially using the following steps:

- If such imputed date for prior therapies is on or after the first dose date, then first dose date - 1 day will be used.
- If such imputed date for subsequent therapies is before date of last dose, then date of last dose +1 day will be used.
- If prior or subsequent therapy start date is not missing and is after the imputed end date, then the start date will be used as the end date.
- If prior or subsequent therapy end date is not missing and is before the imputed start date, then the end date will be used as the start date.

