In addition, for AE date, the above imputations will be modified by the following rules:

- The imputed start date of adverse event will be adjusted sequentially using the following steps:
  - If the imputed date is in the same year and month but before the first dose date, then the first dose date will be used, or if it is in the same year and month but after the last dose date + 30 days, then the last dose date + 30 days will be used.

- If end date of adverse event is not missing and the imputed start date of adverse event is after the end date of adverse event, then the end date of adverse event will be used.
- If the imputed start date of adverse event is after date of death, then the date of death will be used.
- If the imputed start date of adverse event is in the same month and year but after the start date of 1st subsequent therapy, then the start date of 1st subsequent therapy will be used.
- The imputed end date of adverse event will be adjusted sequentially using the following steps:
  - If the imputed end date of adverse event is after the death date, then the death date will be used.
  - If the imputed end date of adverse event is before the start date of adverse event, then the start date of adverse event will be used.

In addition, for start and end dates of concomitant therapy, the adverse event imputation rule will be used for concomitant therapy.

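### The partial-date rule in SAP 6.1 guards only the opening of the TEAE window, so an event whose recorded month or year is already past the window is still treatment-emergent, contrary to the window definition and to SAP 2.10

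*SAP*

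**What the plan says.** **Window.** SAP 6.1 defines TEAEs as events after first dose and "within 30 days following the last dose of study drug or initiation of subsequent antineoplastic treatment, whichever occurs earlier". Two further routes apply whatever the window: events judged drug-related, and baseline conditions that worsen after first dose. Protocol 11.5 has the same definition and no partial-date rule.

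**Partial dates.** SAP 6.1 has a separate rule for any event whose date is incomplete or absent: "then the event will be considered to be treatment emergent unless it is known to be prior to the first administration of study agent". The evidence admitted for that single exception is "based on partial onset date or resolution date".

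**Imputation.** SAP 2.10 separately imputes AE onset dates:
- Day unknown: "If only the day is missing but the year and month are available, then the 15th of the month will be used".
- Month and day unknown: "If only the year is presented but the month and day are missing, then June 30th will be used".
- An AE start date is then adjusted at the end of the window, the limit replacing the imputed date: "if it is in the same year and month but after the last dose date + 30 days, then the last dose date + 30 days will". A parallel adjustment moves it to the start of the first subsequent therapy, again only within the same month and year.

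**Collection.** Protocol 9.4.1 and the Time and Events Schedule stop AE collection 30 days after last dose, while protocol 12.3.1 continues it to the subject's last study-related procedure. Protocol 12.1.5 has new malignancies reported on treatment and "during any protocol-specified follow-up periods including post-progression follow-up for overall survival". SAP 6.1.1 limits the Other Malignancies category to treatment-emergent events.

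**The concern.** The window has two ends and the partial-date sentence protects one. Counting an event as treatment-emergent when its timing is unclear is sound practice. Here, though, the known part of the date can already settle that onset was too late, and the sentence counts the event anyway. The same event with a full date, not judged drug-related, would not be counted. Its status then turns on whether a day of the month was written down.

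The two SAP sections also give different answers for these events, so two programmers could each follow the SAP and produce different TEAE tables. With about 17 subjects, and with data that protocol 1.2 says will support full approval in China, a single case in a rare category such as other malignancies is visible.

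**Working it through.** The documents give no figure for this, so there is nothing to reproduce. The check applies both rules to hypothetical dates.

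**Definitions**
- F = first dose, L = last dose, S = start of subsequent therapy, if any.
- Window end W = the earlier of L + 30 days and S (SAP 6.1). The last day is taken as inside the window.
- Rule A (the SAP 6.1 sentence): TEAE unless the latest date compatible with the record is before F.
- Rule B (SAP 2.10 plus the window): impute, apply the same-month adjustments, then TEAE if the result lies between F and W.
- Known late: the earliest date compatible with the record is after W.

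F is 10 Mar 2020 throughout. No event is judged drug-related or is a worsened baseline condition.

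| Case | L | S | Recorded onset | W | Onset date after 2.10 | Known late? | Rule A | Rule B |
|---|---|---|---|---|---|---|---|---|
| 1 | 1 Mar 2021 | none | Aug 2021 | 31 Mar 2021 | 15 Aug 2021 | yes | TEAE | not |
| 2 | 1 Mar 2021 | 10 Mar 2021 | Apr 2021 | 10 Mar 2021 | 15 Apr 2021 | yes | TEAE | not |
| 3 | 1 Mar 2021 | none | 2022 | 31 Mar 2021 | 30 Jun 2022 | yes | TEAE | not |
| 4 | 20 Feb 2022 | 25 Feb 2022 | Mar 2022 | 25 Feb 2022 | 15 Mar 2022 | yes | TEAE | not |
| 5 | 5 Mar 2021 | none | Apr 2021 | 4 Apr 2021 | 15 Apr, moved to 4 Apr 2021 | no | TEAE | TEAE |
| 6 | 1 Mar 2021 | 10 Mar 2021 | Mar 2021 | 10 Mar 2021 | 15 Mar, moved to 10 Mar 2021 | no | TEAE | TEAE |
| 7 | 1 Mar 2021 | none | Feb 2020 | 31 Mar 2021 | 15 Feb 2020 | no, known early | not | not |
| 8 | 1 Mar 2021 | none | 2021 | 31 Mar 2021 | 30 Jun 2021 | no | TEAE | not |

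**Reading the table**
- Cases 1 to 4 are known to be late, and the rules disagree in all four. In case 1 the earliest possible onset, 1 Aug 2021, is 30 + 31 + 30 + 31 + 1 = 123 days after W.
- Case 4 needs no long follow-up. L + 30 days is 22 Mar 2022, so an onset from 1 to 22 March is inside even the shorter collection period, yet all of March is after W. The last-dose adjustment does not act because 15 March is before 22 March. The therapy adjustment does not act because the month differs.
- Cases 5 and 6 are ambiguous within a month. The adjustments put them inside the window, and the rules agree. They also agree on case 7.
- Case 8 is ambiguous within a year: onset could be January to March 2021, inside the window. Rule A reasonably counts it. Rule B does not, because the adjustments work only within a month. An explicit order of precedence is therefore needed as well as the missing exception.

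**Size.** SAP 6.1 counts subjects with at least one occurrence. With the planned 17 subjects:
- one subject = 1/17 = 5.9%;
- two subjects = 2/17 = 11.8%.

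A preferred term that goes from one to two subjects crosses the 10% cut for the frequency table in SAP 6.1. A subject who already has an event in the category adds nothing.

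**With the extra exception,** cases 1 to 4 become not treatment-emergent, cases 5, 6 and 8 stay treatment-emergent, and case 7 stays excluded.

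**The case against.** **Such events may not be in the data.** Protocol 9.4.1, the schedule and the End of Treatment text in protocol 9.1.3 stop routine AE collection at 30 days. In follow-up, other malignancy sits in a schedule row separate from adverse events, and protocol 12.1.5 describes that reporting as additional to routine AE reporting. The documents do not say these records enter the AE dataset, and they give no rate of partial dates. This stands, and limits the point to events that can occur. Three routes remain: new therapy within 30 days of last dose (case 4), the longer period in protocol 12.3.1, and malignancy reports in follow-up if they are held as AEs.

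**SAP 2.10 may be meant to decide.** Its two adjustments use the same limits as the TEAE window, which suggests that the imputed date was to be compared with the window. On that reading late events are excluded. But the SAP 6.1 sentence is explicit, and nothing ranks the two sections. This supports asking for precedence to be stated; it does not remove the conflict.

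**The bias is conservative.** It can only add events, in a single-arm trial with no safety hypothesis, and listings could show the recorded date. That stands and keeps the weight low. It does not justify counting events that the SAP's own definition excludes.

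**Stronger readings.** A reader might infer that late events are attributed to ibrutinib. The documents do not support this: treatment-emergent is a timing class, relatedness is the investigator's separate judgement (protocol 12.1.2), and drug-related TEAEs have their own table. A reader might also infer that each event adds 5.9 points to every rate. That holds only for a category in which the subject has no other event.

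**Conclusion.** The point holds as a one-sided rule and an unresolved conflict inside the SAP. An event whose partial date already places onset after the window is a TEAE under the SAP 6.1 sentence, but not under the window definition with the SAP 2.10 date.

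The likely effect is small. If 0 to 2 subjects were affected, which is an assumption because the documents give no basis for a count, a category rate would rise by 0 to 11.8 points. The upper figure requires that neither subject has another event in that category. The figures rest on 17 treated subjects, on the window including its last day, and on events that are neither judged drug-related nor worsened baseline conditions. The direction is over-counting. Drug-relatedness judgements and the ORR decision do not change.

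It is a minor correction, worth making because it costs little and settles how the tables are to be programmed.

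**What to change.** In SAP 6.1, add a second exception to the partial-date sentence:

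> *or is known, from the partial onset date, to be after the earlier of last dose + 30 days and the start of subsequent antineoplastic therapy.*

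Then:
- Keep the existing provisions for drug-related events and for worsening of baseline conditions.
- Keep ambiguous and completely missing dates as treatment-emergent, subject to the existing pre-dose exception.
- State that the SAP 6.1 rule decides TEAE status. With the new clause it agrees with the SAP 2.10 date for events known to be late. For ambiguous year-only dates such as case 8, either extend the 2.10 adjustments to the same year when only the year is known, or say that the imputed date does not override 6.1.
- State whether malignancies reported in follow-up are held in the AE dataset, and reconcile the AE collection period in protocol 12.3.1 with 9.4.1 and the schedule. That discrepancy is a separate matter, but it determines how many events the rule can reach.

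The cost of the rule change is one clause, one sentence on precedence and one programming condition. No data collection changes.

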### **6.1.1. AEs of special interest (AESI)**

Number and percent of subjects with following AESIs will be summarized by preferred terms.

#### **Major hemorrhage**

Major hemorrhage is defined as:

- Treatment-emergent hemorrhagic adverse event of Grade 3 or higher. All hemorrhagic events requiring a transfusion of red blood cells should be reported as Grade 3 or higher adverse events per NCI-CTCAE.
- Treatment-emergent SAE of bleeding of any grade
- Treatment-emergent central nervous system hemorrhage/hematoma of any grade

Hemorrhagic events will be identified by hemorrhage Standardized MedDRA Query [SMQ] excluding laboratory terms.

#### **Eye Disorders**

Eye disorders will be obtained from the SOC of “Eye Disorders”.

#### **Other Malignancies**

Treatment-emergent Neoplasms benign, malignant and unspecified (incl cysts and polyps) of any grade (SOC). Relapse of underlying malignancy will not be considered as other malignancies.

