Quantitative serum immunoglobulins (IgA, IgG and IgM)	X	X	X	X	X	X	X	X	X	
Serum free light chain assay	X					Weeks 49 and 97	X			
Bone marrow aspirate and biopsy l	X					Weeks 49 and 97 (± 2 weeks)	X	X		

	Screening Phase	Treatment Phase							Post-Treatment/ Follow-Up Phase	
		1	5-16 q4 weeks	17	21	25+ q8 weeks	Suspected PD Visit	End-of-Treatment Visit a	Post-treatment Pre-disease Progression Phase q12 weeks	Post-disease Progression Phase q12 weeks
Study Weeks		1	5-16 q4 weeks	17	21	25+ q8 weeks	Suspected PD Visit	End-of-Treatment Visit a	Post-treatment Pre-disease Progression Phase q12 weeks	Post-disease Progression Phase q12 weeks
Study Day of the Study Week		1	1	1	1	1				
Study Windows	-30 days		± 3 days		± 3 days	± 3 days	Anytime	± 7 days	± 7 days	± 7 days
CT Scans	X i			X j		X i	X k		X j	
Overall disease assessment			X	X	X	X	X	X	X	
Survival status, new anticancer therapy and occurrence of other malignancy m									X	X
PK sampling										
PK h		X	Weeks 5 and 9							
Ongoing Subject Assessments										
Concomitant medications	X	Continuous from Informed Consent to 30 days after last dose of study drug								
Adverse events	X	Continuous from Informed Consent to 30 days after last dose of study drug								

Abbreviations: aPTT=activated partial thromboplastin time; CR= complete response; CT=computed tomography; DNA=deoxyribonucleic acid; ECG=electrocardiogram; ECOG=Eastern Cooperative Oncology Group; eCRF=electronic case report form; EOT=end-of-treatment; ICF=informed consent form; IEC=Independent Ethics Committee; INR=international normalized ration; IRB=Institutional Review Board; PCR=polymerase chain reaction; PD=progressive disease; PK=pharmacokinetic(s); PO=orally; PT=prothrombin time; q4 weeks=every 4 weeks; q8 weeks=every 8 weeks; q12 weeks=every 12 weeks; REB=research ethics board.

- a. Thirty (30) days from last dose of study drug or prior to the start of a new anticancer treatment.
- b. All subjects must first read, understand, sign and date the IRB/REB/IEC-approved ICF before any study-specific screening procedures are performed.
- c. Physical Examination includes: general appearance of subject, height (screening only) and weight and examination of skin, eyes, ears, nose, throat, lungs, heart, abdomen, extremities, musculoskeletal system, lymphatic system, and nervous system.

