### 1.2. Trial Design

This is a single-arm multicenter, Phase 4 study to evaluate the efficacy and safety of ibrutinib in Chinese subjects with relapsed or refractory WM with symptomatic disease meeting at least 1 of the recommendations from the Second IWWM for requiring treatment.

Approximately 17 subjects will be enrolled into the study. Subjects will receive ibrutinib 420 mg daily until disease progression or unacceptable toxicity, whichever occurs first. Ibrutinib will be supplied as hard gelatin capsules for oral administration.

The study will include a Screening Phase, a Treatment Phase and a Follow-Up Phase. During the Screening Phase, the subjects' eligibility will be determined. The Treatment Phase will extend from first dose of study drug until study drug discontinuation. The Follow-up Phase will consist of the Post-treatment pre-disease progression Phase and a Post-disease Progression Phase. The Post-treatment pre-disease progression Phase will extend from the discontinuation of treatment (for reasons other than disease progression) until the subject has progressive disease, at which point the Post-disease Progression Phase will begin. Subjects who progress on treatment will transition directly to the post disease progression phase. In this latter phase, subsequent anticancer therapy, occurrence of any other malignancy and survival status will be recorded until death, lost to follow-up, consent withdrawal, or study closure. The study is planned to be completed 3 years after the last subject receives first dose.

Clinical cutoffs (CCOs) planned for this study are:

- CCO for the primary analysis is estimated to be performed approximately 12 months after the last subject receives first dose. Alternative appropriate cutoffs will be considered based on regulatory requirement.
- CCO for the final analysis is estimated to occur 3 years after last subject receives first dose.

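### The SAP's Other Malignancies category counts benign tumours, cysts and polyps, and a fully dated, non-fatal late malignancy not judged drug-related has no named summary

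*SAP*

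**What the plan says.** **Definition.** SAP 6.1.1 sets Other Malignancies as "Treatment-emergent Neoplasms benign, malignant and unspecified (incl cysts and polyps) of any grade (SOC"). Its one exclusion is relapse of the underlying malignancy. The opening of SAP 6.1.1 says that the number and percent of subjects with each event of special interest will be tabulated by preferred term.

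**Window.** SAP 6.1 treats an event as treatment-emergent if it occurs after first dose and "within 30 days following the last dose of study drug or initiation of subsequent antineoplastic treatment, whichever occurs earlier". It adds "any adverse event that is considered study drug-related regardless of the start date of the event", and conditions present at baseline that worsen or are later judged drug-related. On dates it says "If the event date is recorded as partial or completely missing, then the event will be considered to be treatment emergent", unless the event is known to precede first dose.

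**Collection.** Protocol 12.1.5 requires that all new malignancies (solid, skin and hematologic) "are to be reported for the duration of study treatment and during any protocol-specified follow-up periods including post-progression follow-up for overall survival". SAP 1.2 says that after progression "subsequent anticancer therapy, occurrence of any other malignancy and survival status will be recorded until death, lost to follow-up, consent withdrawal, or study closure". In the Protocol's Time and Events Schedule, a row "Survival status, new anticancer therapy and occurrence of other malignancy" is marked in both follow-up phases at 12-week intervals.

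**The concern.** The label and the content of the category do not match. A reader of the study report who sees a number of subjects with other malignancies will take it as a number with a second cancer. Under the SAP's definition it can include people with a benign lesion or a polyp.

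The plan also has sites record new malignancies for the whole of follow-up but defines its only malignancy output on a window that closes at most 30 days after the last dose, and earlier if new antineoplastic treatment begins. Some of the cancers that sites are asked to record would then be missing from every named table.

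This matters for this drug and this study. Protocol 1.1.2.3.1 states that non-melanoma skin cancers have occurred with ibrutinib, and Protocol 1.2 says the data are to support full approval in China. The SAP's amendment history shows that version 2 put this category among the events of special interest. What is at stake is the accuracy of a safety count. The overall response rate and its success rule do not depend on it.

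**Working it through.** The plan states no figure on this point, so the check compares definitions and then traces where each kind of event would be reported.

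**1. Which terms count.** The class named in SAP 6.1.1 covers benign, malignant and unspecified neoplasms, with cysts and polyps, by its own title. Only relapse of the underlying disease is taken out. Benign, cyst and polyp terms therefore stay in. Protocol 12.1.5 covers new malignancies only. The SAP does narrow other definitions: for major hemorrhage it drops laboratory terms from the standardized query (6.1.1), and for cytopenias it names preferred terms (6.1.2).

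**2. Where a malignancy with onset after the window would appear.**

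| Late new malignancy | Route in the plan | Named summary? |
|---|---|---|
| Judged drug-related | Treatment-emergent whatever its date (SAP 6.1) | Yes |
| Partial or missing date | Treated as treatment-emergent (SAP 6.1); a partial onset date imputed past the window but in the same month and year is moved back to last dose + 30 days (SAP 2.10) | Yes |
| Fatal | May appear in the death summary by cause (SAP 6.3) | Possibly |
| Serious | Optional listing or narrative (Protocol 11.5) | No, discretionary |
| Fully dated, non-fatal, not judged drug-related | Only the general provision "In addition to the summary tables, listings will be provided as appropriate" (SAP 6.1) | No |

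Every adverse event table named in SAP 6.1 is a treatment-emergent table. SAP 4.5 summarizes subsequent antineoplastic therapy, not the malignancy that may have led to it. The last row therefore has no named output.

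**3. How much off-treatment follow-up the window covers (illustration).** Assume 36 months of follow-up for a subject (3 × 365.25 = 1,095.75 days, with a month of 30.4375 days) and assumed stop times:

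- Stop at month 6: 1,095.75 − 182.625 = 913 days off treatment; 30/913 = 3.3%.
- Stop at month 12: 1,095.75 − 365.25 = 730.5 days; 30/730.5 = 4.1%.
- Stop at month 24: 1,095.75 − 730.5 = 365.25 days; 30/365.25 = 8.2%.

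These are upper limits, because new therapy closes the window sooner. They are shares of off-treatment time only, not of events or of total follow-up.

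**4. Scale per subject.** With about 17 subjects (Protocol 3.1, SAP 1.2): 1/17 = 5.9%, 2/17 = 11.8%, 3/17 = 17.6%. The counts are assumptions.

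**5. Direction (assumed cases, all in different subjects).**

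- One malignancy in the window, no benign event, one late malignancy: the SAP counts 1/17 = 5.9%; new malignancies as Protocol 12.1.5 means them number 2/17 = 11.8%.
- One in the window, two benign events, one late: the SAP counts 3/17 = 17.6%, against 2/17 = 11.8%.

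The two errors act in opposite directions, so the reported figure cannot be assumed conservative.

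**The case against.** **On the benign terms.** The display is by preferred term, so every benign lesion would be named and a reader could separate it. Capture by whole system organ class is also routine in this SAP: eye disorders, hepatic disorders and infections are all built that way. And broad capture hides no cancer. The first argument holds for the individual rows, but SAP 6.1.1 also commits to the number and percent of subjects with the event, and that count would still include benign lesions. The second does not carry over, because those other labels match the classes they draw on and this one does not. The third is true, but it does not make the count correct.

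**On the late cases.** Protocol 12.1.5 and the schedule are duties to report and record; neither promises a table. Protocol 11.5 bases the adverse event analysis on treatment-emergent events and the SAP follows it. This stands, and it is why the second part is a gap and not a contradiction. It also stands that the unreported remainder is narrow once the other routes are taken out. But an optional listing or narrative is not a planned output.

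**On size.** Few late cases are likely. Investigator-assessed progression-free survival in the cited monotherapy data was 83.2% at 18 months (Protocol 1.1.2.2.2) and 64.4% at 30 months in the substudy (Protocol Table 1). Applied to 17 subjects, 17 × 0.168 = 2.9 and 17 × 0.356 = 6.1 would have progressed or died by then. Progression-free survival is not time on treatment, so this is only indicative, but three late, unrelated, non-fatal malignancies would need about half of the larger group or all of the smaller. The top of the illustrative range is therefore improbable for late events.

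**On the cause of the gap.** Protocol 9.4.1 ends adverse event collection 30 days after last dose, while Protocol 12.3.1 continues it to the last study procedure. If the former governs, late malignancies may exist only as follow-up records, and editing the category definition alone would not bring them in. This is a fair point, and the fix has to draw on both sources.

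**Conclusion.** The concern holds in both parts. SAP 6.1.1, applied as written, counts benign neoplasms, cysts and polyps as other malignancies. That is a wrong definition and should be corrected. Separately, a new malignancy that is fully dated, non-fatal, outside the treatment-emergent window and not judged drug-related has no named summary, although it is to be recorded. That is a reporting gap.

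The effect on the reported figure cannot be estimated, because the documents give no rate of benign neoplasms or of late malignancies. The only firm scale is 5.9 percentage points per subject affected, assuming about 17 treated subjects. The conclusion about definitions needs no assumption on rates. The primary endpoint, its confidence interval and the success rule are unaffected. The change should be made, but nothing in the efficacy conclusion turns on it.

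**What to change.** **In SAP 6.1.1,** restrict Other Malignancies to new malignant neoplasms, by a malignancy-specific query or a medically reviewed list of preferred terms. Send unspecified neoplasms for medical review. Exclude benign, cyst and polyp terms, and relapse or progression of Waldenström's macroglobulinemia.

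**Add one count and one listing** of all new malignancies from first dose to end of follow-up, whatever their treatment-emergent status or causality, drawing on the adverse event data and on the follow-up contacts. Identify the treatment-emergent subset, and flag in the listing whether onset came before or after subsequent antineoplastic therapy.

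**Cost.** SAP wording and a small amount of programming, from data already to be recorded. MedDRA coding of follow-up records may be needed, because Protocol 9.4.1 and 12.3.1 disagree on how long adverse events are collected; settle which dataset holds late malignancies first. Late events, especially after other therapy, are harder to attribute to the study drug, which is why the timing flag is needed.
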